7.7 Handling Missing Data in Statistical Analysis

Missing data is a potential problem with any study. All efforts will be made to have a complete and valid data set; however, if the situation occurs, where certain data are missing for a particular subject, the following rules shall be followed:

- If volume (mL) of allogenic RBC transfused and total number of units of blood transfused are both missing for a particular subject, and there is indication for blood transfusion, then the subject with the missing data will be excluded from the relevant analysis. If only one value is missing and the other is valid, then estimation for the missing value will be derived from the valid value.
- Missing other outcomes: subjects with missing outcomes data will be excluded from the relevant analysis.
- Missing Covariates: imputations will be used to account for missing covariates; imputation is the substitution of estimate for a missing data point.

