3.5.1 Primary

To determine whether the addition of SpHb with In Vivo adjustment and RPVi monitoring using the study device will reduce overall allogenic transfusion, where reduction is defined as the decrease in volume of transfusion of the intervention group relative to control group, intra-operatively.

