3.6 Study Outcome Measures

3.6.1 Primary

Volume (mL) of allogenic red blood cells (RBC) transfused intra-operatively.

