6 STUDY PROCEDURES

6.1 Control Group

6.1.1 Retrospective Control Group

Approximately [REDACTED] will be retrospective data collected from the site's medical records. The retrospective data will be collected by designated site personnel only and reported to the sponsor via CRFs.

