Equation 1. Generalized Linear mixed model assessing intervention effect for a given outcome:

$$y_{ij} = (\beta_0 + \gamma_{0j}) + \beta_1 * \text{intervention} + \sum_{k=2}^p \beta_k x_k + \varepsilon_{ij} \quad (1)$$

The outcome, y_{ij} is the value of a response variable for the i^{th} individual of the j^{th} cluster (clinical site).

The betas represent fixed effects for the intercept (β_0), intervention coefficient (β_1), as well as coefficients (β_2, \dots, β_p) for other variables to be included in the model (e.g. demographic and clinical variables). The gamma coefficient (γ_{0j}) represents a cluster-specific random intercept. It is assumed that γ_{0j} has a normal distribution with a mean of zero and a variance of $\sigma_{\gamma_0}^2$.

Type III tests will be used to test the null hypothesis that a specific fixed effect equals zero ($H_0 : \beta_k = 0$). Wald z-tests will be used to test for a significant random intercept ($H_0 : \sigma_{\gamma_0}^2 = 0$). Residual and influence diagnostics will be assessed for all models.

Sequential boundary tolerances will be estimated using Lan & DeMets alpha spending function approach. Statistical analysis will be performed using SAS 9.4 (SAS Institute, Cary, NC)

Table 6. Aims, Outcome Measures and Associated Analysis Planned for those Aims.

Aims/Objectives	Outcome Measures	Planned Statistical Analysis
Reduce overall allogenic transfusion - Volume	Volume of allogenic RBC transfused: Intra operatively	Binomial-Gamma hurdle model. We will include intervention group, demographic and clinical data in the model as progresses.
	Volume of allogenic RBC transfused: Post operatively	

Evaluation of Impacts of Continuous Non-Invasive Intra-operative Hemoglobin and RPVi Monitoring on Intra-operative and Post-Surgical Clinical Outcomes

BIGT0001 version 2

Evaluation of Impacts of Continuous Non-Invasive Intra-operative Hemoglobin and RPVi Monitoring on Intra-operative and Post-Surgical Clinical Outcomes

BIGT0001 version 2

Aims/Objectives	Outcome Measures	Planned Statistical Analysis
[REDACTED]	[REDACTED]	[REDACTED]
	[REDACTED]	
	[REDACTED]	
	[REDACTED]	

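### The missing-data rule for transfused volume excludes subjects according to the primary outcome itself, which lowers each group's transfused share and biases the comparison if such deletion differs between groups

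*Combined protocol and SAP*

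**What the plan says.** The primary outcome (Section 3.6.1) is "Volume (mL) of allogenic red blood cells (RBC) transfused intra-operatively". The primary objective (Section 3.5.1) looks for a lower value under intervention: "reduction is defined as the decrease in volume of transfusion of the intervention group relative to control group, intra-operatively". Table 6 in Section 7.6.2.2 assigns this outcome a "Binomial-Gamma hurdle model". That model has a binomial part for any transfusion and a gamma part for volume among those transfused.

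Section 7.7 has three relevant rules:

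- Volume and units both missing. The trigger is that volume and "total number of units of blood transfused are both missing for a particular subject"; it continues "and there is indication for blood transfusion, then the subject with the missing data will be excluded from the relevant analysis".
- One of the two missing. The subject is kept: "If only one value is missing and the other is valid, then estimation for the missing value will be derived from the valid value".
- Other outcomes. Complete case, with no further condition: "Missing other outcomes: subjects with missing outcomes data will be excluded from the relevant analysis".

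The section does not define indication. It gives no rule for both values missing without an indication, no expected missing rate, no imputation of the outcome when both are missing, and no sensitivity analysis. Missing covariates, by contrast, are imputed.

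**The concern.** The condition about indication has a function only if subjects with both values missing and no indication are treated differently, that is, kept. The rule for other outcomes carries no such condition, which supports this reading. Whether a subject with no recorded amount stays in the analysis then depends on evidence about the outcome. Probable transfusions leave and probable zeros remain.

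If the record shows that blood was given and only the amount is unknown, the subject also carries full information for the binomial part. Excluding that subject from the whole model discards it.

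At stake are the transfused share and mean volume reported for each group and, if deletion is unequal, the primary contrast. Section 7.8 tests that contrast one-sided at 0.05, so a bias toward benefit would raise the false-positive risk. The documents give reasons why deletion could be unequal:

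- Part of the control group is chart review (Section 6.1.1: "The retrospective data will be collected by designated site personnel only and reported to the sponsor via CRFs"), while the intervention phase is entirely prospective (Section 3.2).
- Section 6.2 requires a transfusion threshold to be set before surgery and recorded for intervention subjects. Section 6.1 states no such requirement for controls. If indication means clinical need, it may be easier to establish in the intervention group.

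**Working it through.** Section 7.7 states no figure, so there is none to reproduce. The check derives what the rule does to the estimates.

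**Inputs, all assumed:** p = true share transfused (10-30%; the power inputs are not legible); f = share of transfused subjects with both values missing and hence deleted (1%, 5%, 10%; no rate is stated). Subjects with both values missing and no indication are kept as zero.

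**Step 1, level within a group.** Observed share = p(1 − f)/(1 − pf). If missingness does not depend on the amount given, the overall mean volume scales by (1 − f)/(1 − pf).

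| p | f = 1% | f = 5% | f = 10% |
|---|---|---|---|
| 0.10 | −0.9% | −4.5% | −9.1% |
| 0.20 | −0.8% | −4.0% | −8.2% |
| 0.30 | −0.7% | −3.6% | −7.2% |

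Example: p = 0.20, f = 0.10 gives 0.18/0.98 = 0.184, and 0.184/0.20 is a fall of 8.2%.

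**Step 2, indication read as clinical need.** Suppose 40% are indicated, half of them are transfused (p = 0.20), and 10% of the indicated are deleted. The observed share is 0.20 × 0.90/(1 − 0.40 × 0.10) = 0.1875, a fall of 6.3%. The bias is still downward.

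**Step 3, deleted subjects with atypical volumes.** Let their mean be k times the mean of all transfused subjects. The overall mean scales by (1 − fk)/(1 − pf). At p = 0.20 and f = 0.10, k = 2 gives 0.80/0.98, a fall of 18.4%. The bias vanishes at k = p = 0.20, where the deleted subjects average only the overall group mean. The gamma part is biased only when k differs from 1.

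**Step 4, the contrast.** Deletion multiplies each group's odds of transfusion by (1 − f), so

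observed OR = true OR × (1 − f_int)/(1 − f_ctrl).

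Take p = 0.20 in control and 0.15 in intervention, with equal volume among the transfused. The true OR is (0.15/0.85)/(0.20/0.80) = 0.706 and the true mean ratio is 0.750.

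| Deletion | OR | Mean ratio |
|---|---|---|
| none | 0.706 | 0.750 |
| 10% in both groups | 0.706 | 0.746 |
| 10% in control only | 0.784 | 0.817 |
| 10% in intervention only | 0.635 | 0.685 |

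With no true effect, 10% deletion in one group alone gives an OR of 1/0.90 = 1.11 (control) or 0.90 (intervention). At 1% the corresponding values are 1.01 and 0.99.

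**The case against.** The other side has a good case on four points.

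- **The zeros are inferred.** Section 7.7 never says that subjects without an indication are kept as zero. This stands as a limit on certainty. The alternative is that both kinds of subject are dropped, but then the condition would do nothing.
- **Indication is ambiguous.** A reader might infer that the rule deletes subjects known to have been transfused. The text does not say that. If clinical need is meant, transfusion status is unknown and the claim of full binomial information fails. In addition, the phrase about the relevant analysis might mean the gamma part only, in which case the binomial information is not lost. Both ambiguities stand and need wording.
- **The contrast.** A reader might infer that the rule biases the primary comparison, or tilts it toward the device. The documents do not support this. Equal deletion leaves the odds ratio unchanged and hardly moves the mean ratio. The most obvious mechanism, incomplete control charts, works against the intervention. Unequal documentation of clinical need would work the other way. Neither is quantified.
- **The size.** Deletion needs both values to be missing. Transfused amount is a named CRF item (Section 9.5.2), missing points are queried (Section 9.6.4), and monitors check CRFs for completeness and against source (Sections 10.6 and 10.7). The rate could well be low. Gaps in old charts may be harder to close, but no document gives a figure.

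None of this supplies a reason to keep an exclusion that depends on the outcome.

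**Conclusion.** The point holds in limited form. On the natural reading, Section 7.7 makes exclusion depend on the primary outcome, and this lowers the observed transfused share and overall mean volume within each group. The size is unknown: under 1% relative if 1% of transfused subjects are deleted, and 7.2-9.1% if 10% are, for an assumed 10-30% transfused.

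Bias in the treatment effect is conditional on deletion differing between groups, and its direction cannot be determined from the documents. The gamma part is affected only if missingness depends on the amount given. These conclusions rest on subjects without an indication being kept as zero and on exclusion applying to both parts of the model. The text implies the first and leaves the second open. The rule should be replaced because the remedy is cheap, not because a large error has been shown.

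**What to change.** Rewrite the first rule of Section 7.7 as follows:

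1. Define indication as evidence in the record that allogenic red cells were given intra-operatively.
2. Where there is such evidence but neither volume nor units, keep the subject in the binomial part as transfused. Multiply impute a positive volume for the gamma part from variables already collected, such as group, site, surgery type and intra-operative hemoglobin (Section 6.5). Use blood loss only if it is on the CRF, since it is not among the items listed in Section 9.5.2.
3. Where transfusion status is unknown, treat it as missing and impute it. Assign zero only when the record supports no transfusion.
4. Add a sensitivity analysis with low and high plausible volumes, or a tipping-point analysis.
5. Report the number of such subjects by group, with retrospective and prospective controls shown separately.

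The cost is SAP wording and one imputation step, with no new patients. The result will rely to some extent on the imputation model, which the sensitivity analysis is there to test.

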7.8 Interim Analysis decisions

The interim analysis will be performed after collecting data on 281 subjects in the intervention group and 562 subjects in the control group.

The Lan-DeMets bounds using O'Brien-Fleming spending function was utilized to calculate the spending alpha. The Overall alpha is 0.05 and One-Sided Bounds

Table 7. Adjusted Alpha and Boundary Results

Analysis	Time	Upper Boundary	Adjusted Alpha	Cumulative Alpha
Interim	0.5	2.5380	0.0056	0.0056
Final	1	1.6621	0.0444	0.0500

Interim Analysis results will be presented to the principal investigators, the sponsor, and the DSMB for evaluation and decision-making.

7.9 Early Stopping Rules

- Upon review of occurrence of unanticipated adverse device effects and/or other harmful events as a direct result of the clinical investigational procedures, principal investigators, sponsor, and DSMB may decide to terminate the study to safeguard subject safety.
- If the results of the interim analysis show a statistically significant result relating to the outcome measures, then the principal investigators, sponsor, and DSMB may decide to terminate the study.

8 SAFETY AND ADVERSE EVENTS

8.1 Definitions

The definitions for adverse event, adverse device effect, serious adverse event, serious adverse device effect, and unanticipated adverse device effect are provided below (ISO 14155:2011, 21 CFR 812.3(s)).

- Adverse Event (AE): an adverse event is any untoward medical occurrence in a subject which need not be related to the device under investigation.
- Adverse Device Effect (ADE): an adverse device effect is any untoward or unintended response to a medical device which may result from insufficiencies in the instructions for use or deployment of the device, or from use error.
- Serious Adverse Event (SAE): a serious adverse event is an adverse event that results in death, inpatient hospitalization, severe or permanent disability, a life threatening illness or injury, fetal distress, fetal death, a congenital abnormality, a birth defect, or medical or surgical intervention to prevent permanent impairment to body or structure.
- Serious Adverse Device Effect (SADE): a serious adverse device effect is an adverse device effect that results in death, inpatient hospitalization, severe or permanent disability or is life threatening.
- Unanticipated Adverse Device Effect (UADE): any serious adverse effect on health or safety or any life threatening problem or death cause by or associated with, a device, if the effect, problem, or death was not previously identified in nature, severity or degree of incidence in the investigational plan, or application (including a supplementary plan or application) or any other unanticipated serious problem associated with a device that related to the rights, safety or welfare of subjects. Refer to the Device Risk Analysis and Risk Assessment section for details on anticipated adverse device effects.

8.2 Anticipated Adverse Events:

- Mild allergic reaction to sensor material and adhesives.
- Low risk of thermal burn from sensor LEDs.
- Low risk of pressure damage if sensors are applied too tightly.

AEs related to surgical procedures are not listed in this CIP.

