3.4 Hypothesis

[figure not shown]
The addition of real-time, continuous, noninvasive, intra-operative SpHb with In Vivo adjustment and RPVi monitoring via study devices to current hospital standard of care parameters will lead to reduction of total volume of blood transfusions during major surgical procedures. Reduction in total blood transfusion will in turn lead to reduction of complications related to blood transfusions thus shortening length of stay (LOS) for patients and improving clinical outcomes. The real-time, continuous In Vivo SpHb and RPVi data will help shorten the time between detection of patients' changing hemoglobin and fluid status and subsequent clinical decisions for transfusion and infusion.

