5.2 Inclusion Criteria

- Adult patients undergoing major surgeries associated with possibility of significant blood loss (e.g. such that blood is cross-matched and available before the start of the case as per hospital routine practice) under general anesthesia.
- At least one finger available and accessible for performing non-invasive hemoglobin monitoring.

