11.2 Sponsor Responsibilities

Sponsor responsibilities are outlined by the DSMB Charter, which include but are not limited to the following:

- Assure the proper conduct of the study;
- Assure collection of accurate and timely data;
- Compile and report Serious Adverse Events (SAEs), Serious Adverse Device Effects (SADEs), and Unanticipated Adverse Device Effects (UADEs) to the DSMB;
- Report safety concern(s) to the DSMB;
- Prepare summary reports of relevant data for the DSMB, if requested;
- Communicate with regulatory authorities, IRB/EC, and investigators, in a manner that maintains integrity of the data, as necessary.

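### Section 8.1 does not count a prolonged hospital stay as serious in surgical inpatients, and its SADE criteria are narrower than its SAE criteria

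*Combined protocol and SAP*

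**What the plan says.** Section 8.1 (Definitions) says that "a serious adverse event is an adverse event that results in death, inpatient hospitalization, severe or permanent disability, a life threatening illness or injury". After these come four fetal or congenital items and, finally, "medical or surgical intervention to prevent permanent impairment to body or structure". It defines a SADE as "an adverse device effect that results in death, inpatient hospitalization, severe or permanent disability or is life threatening". Neither definition mentions prolongation of an existing hospital stay, and no other legible section adds it. Nothing says how the planned surgical admission is to be treated.

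The population is described in 5.2 as "Adult patients undergoing major surgeries associated with possibility of significant blood loss", under general anesthesia. Section 3.1 says that prospective subjects come from hospital patients already scheduled for surgery.

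Under 8.3.1 the principal investigator at each site decides whether an event meets the SAE criteria. The resulting classes are used in three places:

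- Section 3.7 collects AE, SAE and UADE counts for each study group.
- Section 11.2 requires the sponsor to "Compile and report Serious Adverse Events (SAEs), Serious Adverse Device Effects (SADEs), and Unanticipated Adverse Device Effects (UADEs) to the DSMB".
- Section 8.5 makes every SAE at an EU site reportable to the national competent authorities.

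**The concern.** A hospitalization criterion captures events that bring a patient into hospital. In this trial the subject is normally in hospital when a perioperative event occurs, so before discharge the criterion catches nothing if taken at its word. The usual serious consequence of a moderate surgical complication, a longer stay, is then not named at all. The omission is awkward here because the hypothesis in 3.4 has fewer transfusion complications "thus shortening length of stay (LOS) for patients and improving clinical outcomes". A complication that lengthens the stay is the opposite result, and the definitions do not recognise it as serious.

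At stake is the SAE class in three uses: the count by group, what the DSMB sees as serious, and expedited reporting at EU sites. Section 3.1 also has each site enrol all its controls before its intervention subjects. If a site's way of grading these events changed over time, the change would tend to fall along the control/intervention boundary.

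The second issue is one of internal consistency. A serious adverse device effect should be a device effect that is serious by the protocol's own standard. As written, SAE and SADE use two different standards.

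**Working it through.** No arithmetic on power or error rates applies. The check is to set the two lists in 8.1 side by side and then follow two kinds of event through the sections that use the classes.

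| Criterion in 8.1 | SAE | SADE |
|---|---|---|
| Death | yes | yes |
| Inpatient hospitalization | yes | yes |
| Severe or permanent disability | yes | yes |
| Life-threatening | yes | yes |
| Four fetal or congenital items | yes | no |
| Intervention against permanent impairment | yes | no |
| Prolongation of an existing stay | no | no |

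The SAE list has 4 + 4 + 1 = 9 criteria and the SADE list has 4, a difference of 9 − 4 = 5. Four of those 5 are fetal or congenital and have almost no effect, because 5.3 excludes pregnant patients. That leaves 5 − 4 = 1 difference of substance: the intervention criterion.

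**Event A: a complication before discharge whose only serious consequence is a longer stay.**

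1. It is not fatal, life-threatening or disabling, and needed no intervention against permanent impairment. It did not cause the admission. Under 8.1 it meets no SAE criterion.
2. It is entered in the Adverse Event Log (8.3), because all AEs are.
3. The detailed report form (8.4.1) covers device-related events and SAEs. An unrelated event graded non-serious falls outside it.
4. In 3.7 it is absent from the SAE count for its group but present in the AE count. The between-group comparison that 3.7 names is of AE occurrences, so the event stays in that comparison.
5. It is not in the SAE reports under 11.2. It may still appear among the AEs in the DSMB reports described in 11.4.
6. At an EU site the clocks in 8.5 do not start. They are 3 calendar days from site to sponsor, then 2 or 7 calendar days from sponsor to authority.

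**Event B: a device-caused injury that meets only the intervention criterion.**

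1. It is an SAE under 8.1 but not a SADE.
2. It goes to the DSMB as an SAE (11.2), is documented in detail as device-related (8.4.1), and is reportable as an SAE at EU sites (8.5).
3. It may be a UADE. That definition speaks of serious adverse effects generally and is not tied to the SADE list.
4. No count in 3.7, stopping rule in 7.9 or reporting clock in 8.4 or 8.5 turns on SADE status. What changes is the SADE listing under 11.2.

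**The case against.** The best defence is that little is lost. Every AE is logged with enough information to judge seriousness (8.3), monitors check SAE and SADE documentation at each visit (10.7), and events can be regraded later. Much of this stands. Later regrading, however, cannot recover an EU reporting deadline or a DSMB meeting that has passed, and monitors checking against 8.1 would be applying the same list.

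Section 8.1 also cites ISO 14155:2011 for its definitions, and the report form, CRF sample and DSMB charter are not visible. One of them might deal with prolonged stay. That cannot be checked here. The protocol text is nevertheless what it gives investigators as the criteria, so it should be complete in itself.

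Several stronger readings are tempting but not supported:

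- *The hospitalization criterion fails altogether, so serious events in general are misclassified.* Follow-up runs to a call at day 30 to 40 (6.7), and a readmission plainly counts as hospitalization. Fatal, life-threatening and disabling events, and those meeting the intervention criterion, remain SAEs in an inpatient. Only events whose sole serious consequence is a longer stay are affected.
- *Some sites will grade almost every in-hospital event as serious.* The wording is causal: the event must result in hospitalization. Nothing in the documents suggests that sites would read it so loosely.
- *SADE counts enter the safety comparison in 3.7.* They are not listed there.
- *A serious sensor burn escapes UADE status because 8.2 lists burns as anticipated.* UADE status also depends on severity and degree of incidence. Section 8.2 lists only a low risk of thermal burn and states no severity. Section 8.1 also refers to a risk analysis section that is not in the text available.
- *The number of affected subjects can be estimated.* Taking 2304/3 = 768 intervention subjects and an assumed share of 5% to 20% gives 38 to 154. The documents give no basis for the share, and the final group split is not legible. The interim total, 281 + 562 = 843 at information time 0.5 (7.8), would imply 843/0.5 = 1686 subjects, not 2304, so carrying the interim ratio over to 2304 is not secure either.

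**Conclusion.** The point holds in limited form. Two defects are visible in 8.1 itself.

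First, as the rule is worded, a complication before discharge whose only serious consequence is a longer stay is non-serious. It leaves the per-group SAE count, the SAE reports to the DSMB and EU SAE reporting. It remains a logged AE and stays in the overall AE comparison. This rests on a literal reading of 8.1 and on no unseen document supplying the missing criterion.

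Second, the SADE list omits one SAE criterion that matters in this population. The practical effect is confined to the SADE listing.

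The number of events involved cannot be derived from the documents. The primary outcome (intra-operative red-cell volume), alpha and sample size are not affected. The sponsor should correct this because the remedy is cheap and the SAE class has reporting consequences; it does not threaten the trial's main conclusion.

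**What to change.** Amend 8.1 in three respects:

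- Add prolongation of the existing hospitalization to the SAE criteria, beside inpatient hospitalization.
- State that the planned surgical admission is not itself an SAE.
- Define SADE as any adverse device effect that meets any SAE criterion, so that a single list serves both classes.

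This takes two or three sentences in an amendment and a short training note to the six sites, so that investigators grade alike across sites and across the control and intervention phases. If subjects have already been enrolled, logged AEs should be regraded under the amended wording in both groups. The downside is somewhat more SAE reports, including expedited ones at EU sites. No change to the primary analysis is needed.
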